**Possible Risk (mention if there is any risk or not):**

No possible risk.

**Primary outcomes** (Most important outcomes to be assessed)

1- End to start facial nerve MEP amplitude ratio.

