#### 4. Background and Rationale:

The well-accepted goals for the anaesthetic management of patients undergoing neurosurgical procedures include the delivery of smooth and hemodynamically stable anaesthesia with provision of good operating conditions and a smooth but rapid emergence that allows for early neurological assessment.(1)

Muscle relaxation is considered as elements of general anaesthesia. Neuromuscular blocking agents (NMBAs) are usually administered during anaesthesia to facilitate endotracheal intubation and/or to improve surgical conditions.

The use of NMDs for general anaesthesia may cause many side effects, which cannot be ignored, such as residual paralysis, delayed recovery from general anaesthesia, recurarization, anaphylactic or anaphylactoid reactions, histamine release, all of which need to be reversed. At last but not least it interferes with the neurophysiologic

monitoring of these patients. (2)

Now we can use nerve stimulator device for easily monitoring of administration of and recovery from neuromuscular blocking agents (NMBAs) whenever possible is recommended.

We agree with the guidelines issued by the Association of Anaesthetists of Great Britain and Ireland (AAGBI) statements that a peripheral nerve stimulator is mandatory when NMBAs are used (3).

Intraoperative neurophysiological monitoring has been established as one of the paths by which modern neurosurgery can improve surgical results while minimizing morbidity. This proceeding consists of the monitoring of functional integrity of the neural pathways and mapping of techniques for identification and preservation of the cranial nerves, their motor nuclei, and corticospinal or corticobulbar pathways during posterior-fossa and brainstem surgery.(4)

During these surgical procedures, small injuries can produce significant neurological deficits, and therefore global integrity of the brainstem must be monitored through transcranial electric motor-evoked potentials (TceMEPs). (5,6)

Preservation of facial nerve (FN) function is a well-recognized goal of tumor excision at the cerebellopontine angle (CPA). Especially in cases of vestibular schwannoma excision, postoperative facial paresis and paralysis may occur despite efforts to avoid injury and maintain anatomic integrity of the nerve during dissection.(9)

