### **Methodology in details :**

Before induction of anaesthesia and Before Rocronium administration, the baseline twitch response will be established with a neuromuscular nerve stimulator (NMT mechanosensor, GE healthcare, Helsinki, Finland) to achieve the maximum response of the adductor pollicise muscle.

The maximum electromyography amplitude of T1 before Rocronium administration will be considered to be the control response (Tc). The response of the adductor pollicise brevis muscle to TOF stimulation of the ulnar nerve will be monitored every 5 min and will be recorded every 30 min, and the infusion dose of Rocronium will be adjusted according to the target of the partial NMB group.

Anaesthesia will be induced by I.V. propofol (1.5-2 mg/kg) with fentanyl (2–4 mcg/kg) through syringe infusion pump. After induction, tracheal intubation will be facilitated with Rocronium (0.6 mg/kg).

Anaesthesia will be maintained by propofol and fentanyl infusions through the pump. Subjects will be randomly allocated into one of the two groups:

Group A (n=20): will receive Rocronium as muscle relaxant, maintain partial NMB T2/TC 0.5 or TOF count 2 (10) , Fentanyl will be infused at a dose range of 0.5–1mcg/kg/hr. to control the haemodynamic response to the surgical procedure within a 20% range of its preoperative value, and propofol will be infused at a dose range of 6–8 mg/kg/hr. to targeting Bispectral index at 40 -60.(11)

Group B (n=20): will not receive muscle relaxant, Fentanyl will be infused at a dose range of 0.5–1mcg/kg/hr. to control the haemodynamic response to the surgical procedure within a 20% range of its preoperative value, and

propofol will be infused at a dose range of 8–12 mg/kg/hr. to targeting Bispectral index at 25-35, after ending of monitoring of neurophysiology propofol dose will be dropped to 4–6 mg/kg/hr. targeting Bispectral index 40- 60.(11)

The mean arterial pressure during the surgery will be monitored every 5 min and will be recorded every 30 min and will be compared between the groups. Hypotension will be defined as a decrease in the mean arterial pressure of more than 20% of the preoperative value or below 55 mm Hg and will be treated by repeated 5 mg I.V. ephedrine bolus doses. Vasopressor infusion (norepinephrine in starting dose of 0.3 up to 2 mcg/kg/min) will be given if three or more ephedrine bolus doses is required. If bradycardia (60 beats min) developed, 0.6 mg of atropine will be administered.

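### The nil-risk statement contradicts the protocol's own background and methods, and allergic-type reactions, bradycardia episodes and residual or recurrent block have no planned event count

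*Combined protocol and SAP*

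**What the plan says.** The field headed "Possible Risk (mention if there is any risk or not" is answered "No possible risk". Nothing in the field or its answer limits it to risk added by the research.

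Section 4, Background and Rationale, says that relaxants "may cause many side effects, which cannot be ignored, such as residual paralysis, delayed recovery from general anaesthesia, recurarization, anaphylactic or anaphylactoid reactions, histamine release". It adds that they interfere with neurophysiological monitoring, which is what the primary outcome addresses.

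Methodology in details states that "tracheal intubation will be facilitated with Rocronium (0.6 mg/kg" before the two groups are described. Group A then stays under partial block. The same section says: "Hypotension will be defined as a decrease in the mean arterial pressure of more than 20% of the preoperative value or below 55 mm Hg", with a treatment sequence. It also says: "If bradycardia (60 beats min) developed, 0.6 mg of atropine will be administered".

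Three places plan recording that bears on these harms:

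- Measurement tools covers train-of-four ratio (TOFr) to 1 hour after extubation (item 2), heart rate and blood pressure (item 3), drug totals (item 4), hypotensive episodes and vasopressor doses (item 5) and eye-opening time (item 6).
- The secondary outcomes include the recovery profile, and hypotension episodes with vasopressor use.
- The extubation criteria require a TOF ratio above 0.9.

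**The concern.** A protocol cannot call a drug class's side effects too important to ignore, plan treatment for circulatory events, and also say that no risk is possible. The risk field is where someone assessing the trial would look, and its answer conflicts with two other sections.

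The second issue is what the trial will be able to report. Recovery and haemodynamics are stated objectives alongside the MEP comparison. A conclusion favouring partial block or no block would have to be weighed against the harms of each. If some of the harms that the protocol names are never recorded as events, that comparison will be incomplete, and silence in the report could be mistaken for absence.

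**Working it through.** No arithmetic applies, and the plan's sample-size figure is not an input. The check sets each named harm against every place where recording is planned.

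| Harm | Named in | Planned recording | Status |
|---|---|---|---|
| Delayed recovery | Background | Secondary outcome 1; Measurement tools item 6 | Outcome |
| Residual paralysis | Background | TOFr (Measurement tools item 2); TOF ratio above 0.9 to extubate | Indirect; not defined or counted as an event |
| Recurarization | Background | TOFr to 1 hour after extubation | Indirect; not defined or counted as an event |
| Anaphylactic or anaphylactoid reaction | Background | None found | Not recorded |
| Histamine release | Background | None found | Not recorded |
| Hypotension | Methodology | Measurement tools item 5; secondary outcome 3 | Outcome |
| Bradycardia | Methodology | Heart rate, every 30 minutes after incision (Measurement tools item 3) | Episodes and atropine use not counted |

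**Tally.** Of the five Background harms, 1 is an outcome, 2 are covered indirectly and 2 are not recorded. Of the two Methodology harms, 1 is an outcome and 1 is only partly captured. Over all seven: 2 outcomes, 2 indirect, 1 partial, 2 absent (2 + 2 + 1 + 2 = 7).

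**Bradycardia.** Heart rate is watched every 5 minutes but written down every 30, so a brief episode treated between recorded points could leave no trace. The drug totals in item 4 cover propofol, fentanyl, ephedrine and norepinephrine. Atropine is not among them.

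**Residual and recurrent block.** The raw measurement exists. Item 2 records TOFr, and the extubation criteria supply a threshold. What is missing is a rule that turns the readings into a yes-or-no event for each patient. Item 2 does not name extubation itself as a recording time, although the criterion means that the value must be read then.

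**General adverse events.** No section describes collecting them, so nothing else would pick up the unrecorded items.

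**Which arms are exposed.** Study Methods describes induction with a single dose of a relaxant, and Methodology gives rocuronium for intubation, both before the groups are separated. Group B is then said not to receive relaxant. The natural reading is that both arms are exposed at intubation and only Group A afterwards.

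**The case against.** The best defence is that the one-line answer means no risk beyond ordinary care. The Background describes intravenous anaesthesia with no relaxant, or with shallow block, as the current standard for MEP-monitored neurosurgery, so both arms resemble usual practice. This makes loose wording the likely explanation. It does not rescue the statement: the field asks about any risk, and no section limits the answer. Randomisation also decides which patients have continued relaxant (Group A) and which have the BIS target of 25-35 rather than 40-60 during monitoring (Group B).

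A second objection is that much is already measured. That is correct and limits the point. A reader might infer from the nil-risk statement that all the named harms go uncounted. The documents do not support this: hypotension is counted in two places, delayed recovery is a secondary outcome, and TOFr is followed after extubation.

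Three other inferences also go too far:

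- *That declaring no risk caused the gaps.* No section links the two, and the same protocol made hypotension and recovery outcomes.
- *That relaxant harms concern Group A alone.* The intubation text reads otherwise.
- *That participants or an ethics committee were misled.* The ethics section is only a departmental approval field, and consent pages are not in the material reviewed.

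**Conclusion.** The risk statement is wrong by the protocol's own text and must be reconciled with the Background and the Methodology. The recording gap is real but partial. Two of the seven named harms have no planned recording, bradycardia has no count of episodes or atropine use, and residual and recurrent block are measured but not defined or counted as events.

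This is a correction that should be made, not a flaw in the comparison. The primary outcome, its analysis and the sample size are unaffected. The verdict rests on two readings: that the risk field is unrestricted, as its wording indicates, and that relaxant at intubation applies to both arms. If Group B were in fact to receive none at all, the intubation text would need correcting and the list of exposed patients would change. The contradiction would remain.

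**What to change.** 1. **Risk statement.** Replace it with the risks that the protocol already names. List the Background's relaxant harms for both arms, noting continued exposure in Group A, and hypotension and bradycardia for both arms. Limiting relaxant harms to Group A would create a new contradiction with the intubation text.
2. **Event record.** Add to Measurement tools, by arm and until PACU discharge: allergic or anaphylactoid reactions, including suspected histamine reactions; bradycardia episodes by the protocol's own trigger; atropine use; and residual or recurrent block. Judge block from the TOFr readings already planned, against the protocol's own 0.9 extubation threshold, and write down the value read at extubation. Define each event before recruitment so that counts are consistent.
3. **Reporting.** Give the number of patients with each event by arm, with exact 95% confidence intervals. With 20 per arm these will be wide and should be treated as descriptive. Hypotension and recovery need no new data.
4. **Participant information.** If any of it repeats the nil-risk statement, bring it into line.

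The cost is a text correction and a short checklist completed by staff already present. No treatment, procedure, primary analysis or sample size changes.

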**Secondary outcome parameters (other outcomes to be assessed)**

1- Recovery profile ((time to eye opening, extubation, orientation, obeying commands, and an Aldrete score >9)) , [Time Frame: every 10 min for 1 hour at PACU.]

2- Total volume of propofol infused

3- BP , number of hypotension episodes and use of vasopressors

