Intraoperative monitoring included continuous ECG, pulse oximetry, arterial pressure (via arterial line and non-invasive arterial pressure cuff) ,temperature to avoid hypothermia ,The monitoring of transcranial electrophysiology for surgery will be performed by recording MEP, bispectral index (Covidien, Aspect medical systems, inc, Norwood, USA ) and train of four.

TCMEP monitoring of the facial nerve will be performed using two stimulant corkscrew scalp electrodes (NIM Eclipse, Midtronic) placed at positions C3 and C4 (International 10–20 EEG electrode system) Potentials will be recorded from paired sub dermal needle electrodes placed in the orbicularis oris and oculi . intraoperative monitoring for all patient will be performed by a same operator .

TCMEP recording will begin (1) prior to skin incision as baseline amplitude before muscle relaxant be taken for intubation (2) at Dural closure and end \start amplitude ratio will be calculated.

After the end of surgery, anaesthetic drugs will be stopped The extubation criteria are as follows: TOF ratio > 0.9, BIS > 70, regular respiratory pattern, tidal volume of at least 5 ml/kg and SpO2 > 95% when the patient breathes spontaneously.

The patient will be sent to the PACU while the neurosurgeons will assess appearance of neurological dysfunction.

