#### Measurement tools

1- Duration of the surgery from skin incision till skin closure will be recorded. And duration of anaesthesia from intubation till closure of anaesthetic agent.

2- TOFr and BIS will be monitored continuously every 5 min and will be recorded at baseline, at intubation, at skin incision, 30 and 60 minutes after skin incision, every 30min and 1 hr after extubation.

3- Intraoperative mean blood pressure and heart rate will be monitored every 5 min and will recorded in all groups immediately after induction, at surgical incision and every 30 minutes till the end of procedure.

4- Total amount of intraoperative propofol, fentanyl, ephedrine and norepinephrine consumption will be recorded

5- Number of hypotensive episodes, and required doses of ephedrine and vasopressors ( norepinephrine in starting dose of 0.3 up to 2 mcg/kg/min)

6- The eye-opening time (defined as the period from the cessation of propofol-fentanyl administration to when the patient opened his/her eyes on command)

7- Facial nerve function will be evaluated pre-operatively, immediately postoperatively.

8- Ratio of end operative to start-operative FMEP amplitude will be monitored .

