### **Sample size (number of participants included)**

We calculated our sample size using G-power software. Our primary outcome is end to start facial nerve MEP ratio was derived from a previous study to be mean  $0.72 \pm 0.43$  calculated by using previous results (12) with SPSS program. We assumed that ratio will decrease 50%. Considering a study power of 80% and a p-value of 0.05 to be significant, the sample size was calculated to be 38 patients (19 in each group). To compensate for drop-out we will recruit 20 patients in each group.

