### **Statistical analysis:**

Data will be coded and entered using the statistical package SPSS version 24. Data will be summarized using mean and standard deviation for quantitative variables and frequencies (number of cases) and relative frequencies (percentages) for categorical variables. Comparisons between groups will be done using unpaired t test when comparing 2 groups and analysis of variance (ANOVA) with multiple comparisons post hoc test when comparing more than 2 groups (13). For comparing categorical data, Chi square ( $\chi^2$ ) test will be performed. Exact test will be used instead when the expected frequency is less than 5 (14). Correlations between quantitative variables will be done using Pearson correlation coefficient (15). P-values less than 0.05 will be considered as statistically significant.

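### Time to an Aldrete score above 9 is observed for only 1 hour but compared by a t test on mean times, with no rule for patients who have not reached the target

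*Combined protocol and SAP*

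**What the plan says.** Under Secondary outcome parameters, the recovery profile covers "time to eye opening, extubation, orientation, obeying commands", followed by the Aldrete item and its window: "and an Aldrete score >9)) , [Time Frame: every 10 min for 1 hour at PACU". That gives six scheduled looks, the last at 60 min.

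Under Statistical analysis, "Data will be summarized using mean and standard deviation for quantitative variables", and "Comparisons between groups will be done using unpaired t test when comparing 2 groups". No time-to-event, rank or other censored-data method appears, and no analysis of the proportion at target by the last check. No section says what value a patient receives who is still below the target then.

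A time origin is given for eye opening only, in Measurement tools: "defined as the period from the cessation of propofol-fentanyl administration to when the patient opened his/her eyes on command". In Methodology in details, the extubation criteria come first and PACU follows: "The patient will be sent to the PACU while the neurosurgeons will assess appearance of neurological dysfunction". The documents do not print the range or steps of the Aldrete score.

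**The concern.** A time to a threshold, watched through a fixed window, has no observed value for anyone who does not cross the threshold inside the window. A mean and a t test need a number for every patient. The analyst must therefore either leave those patients out or enter a substitute such as 60 min, and the plan chooses neither. Leaving them out selects on the outcome. Entering 60 treats a patient still short of the target the same as one who reached it at the last look.

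This matters here because recovery is a stated objective and the arms are run at different BIS targets and propofol ranges by design, so the share of late recoverers may differ by arm. With 20 patients per arm, a few missing times in one arm carry weight. A choice made after the data are seen also leaves room for discretion.

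**Working it through.** The plan gives no figure for the recovery outcome, so there is none to reproduce; its sample size concerns the MEP amplitude ratio and does not bear on this point.

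**Inputs from the documents:** looks every 10 min, last look at 60 min, 20 patients per arm, comparison of means by unpaired t test.

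**Assumptions (not in the documents):** log-normal times with median m and log-SD s = 0.4 in both arms, measured from the start of the 1-hour window and rounded up to the next look.

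**Formulas.** F(t) = Φ(ln(t/m)/s), and p_k = F(10k) − F(10(k−1)) is the chance of first meeting the target at look k.
- Share not reached: 1 − F(60)
- Full mean: Σ 10k·p_k over all k
- Mean after dropping: Σ 10k·p_k for k ≤ 6, divided by F(60)
- Mean with 60 entered: Σ 10k·p_k for k ≤ 6, plus 60·(1 − F(60))

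**Medians 40 and 55 min.**
- Not reached: 1 − Φ(ln(60/40)/0.4) = 1 − Φ(1.014) = 0.155, and 1 − Φ(ln(60/55)/0.4) = 1 − Φ(0.218) = 0.414.
- Full means 48.3 and 64.6: difference 16.3.
- Dropped: 42.4 and 48.2, difference 5.9.
- 60 entered: 45.1 and 53.1, difference 8.0.

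**Medians 30 and 45 min.**
- Not reached: 0.042 and 0.236.
- Full means 37.5 and 53.75: difference 16.25, shown as 16.3.
- Dropped: 35.8 and 44.7, difference 9.0.
- 60 entered: 36.8 and 48.3, difference 11.6.

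The same formulas give the lower rows:

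| Medians (min) | Not reached by 60 min | Full difference | Dropped | 60 entered |
|---|---|---|---|---|
| 40 / 55 | 15.5% / 41% | 16.3 | 5.9 | 8.0 |
| 30 / 45 | 4% / 24% | 16.3 | 9.0 | 11.6 |
| 20 / 30 | 0.3% / 4% | 10.8 | 9.2 | 10.1 |
| 15 / 22 | 0% / 0.6% | 7.5 | 7.3 | 7.5 |

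Shrinkage from dropping is (16.3 − 5.9)/16.3 = 64%, (16.3 − 9.0)/16.3 = 45%, (10.8 − 9.2)/10.8 = 15% and (7.5 − 7.3)/7.5 = 3%.

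**Power**, simulated at 20 per arm and two-sided 0.05. The last column is a rank test on the same scores with not-reached patients ranked worst.

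| Medians (min) | t test, full times | t test, dropped | t test, 60 entered | Rank test |
|---|---|---|---|---|
| 40 / 55 | 0.65 | 0.29 | 0.61 | 0.63 |
| 30 / 45 | 0.84 | 0.63 | 0.85 | 0.85 |

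**Unequal spread** (continuous times, medians 30 and 40 min, log-SD 0.7 and 0.3).
- True means are 30·exp(0.7²/2) = 38.3 and 40·exp(0.3²/2) = 41.8, a difference of 3.5.
- Among those at or below 60 min the means are 28.1 and 39.2, a difference of 11.1. Here dropping enlarges the difference.

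**Equal arms.** With the same median and spread in both arms, the difference is 0 and the rejection rate after dropping is about 0.05.

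**The case against.** The documents contain no recovery times and no distribution of Aldrete scores. Eligible patients are ASA I-II with GCS 15 and without cardiac disease, and they reach PACU after meeting extubation criteria on BIS and TOF ratio. If nearly all reach the target well inside the hour, the t test does little harm, as the 15/22 row shows. This stands: the size cannot be settled from the plan. The documents do not show that recovery is quick either, so the gap is not closed.

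Four stronger readings are tempting and are not supported.
- A reader might infer that the bias always runs toward no difference. That needs a material share beyond 60 min, more of them in the slower arm, and similar spread; the unequal-spread example goes the other way.
- A reader might infer that >9 admits only the top score, so that unreached patients must be common. The first part holds on an assumed whole-number 0-10 scale, which the documents do not print. The second has no support in any figure given. The gap exists whatever the scale.
- A reader might infer that entering 60 min removes the slow patients. It keeps them. It compresses their times, and in these scenarios it costs little power although the estimated difference is too small.
- A reader might infer that the whole recovery objective is biased. Eye opening is timed from drug cessation and extubation precedes PACU, so the PACU window does not plausibly truncate those two.

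**Conclusion.** The point holds as a mismatch between one secondary outcome and its planned test. The window is fixed, the outcome is a time to threshold, and the stated method cannot use a patient who has not crossed it. It concerns the Aldrete item and possibly orientation and obeying commands. The primary outcome and its sample size are unaffected.

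Under the assumed log-normal model with equal spread, dropping unreached patients costs between 3% and 64% of the mean difference across the scenarios shown, depending on how many exceed 1 hour. The direction can reverse if the arms differ in spread. These medians and spreads are assumptions chosen to show the range; the trial's own position within it is unknown. Because a suitable analysis uses the same scores, the change is worth making before data are seen.

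**What to change.** For the Aldrete item, and for orientation and obeying commands if they are recorded in the same window:

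1. Replace the t test by Kaplan-Meier curves with a log-rank test, censoring at the last PACU check. A rank test with not-reached patients ranked worst is an acceptable alternative. Name one of them in advance.
2. Report, for each arm, the number and proportion at the target by the 1-hour check.
3. State the time origin. PACU arrival would match the 1-hour window; if time runs from drug cessation, the censoring time differs between patients and must be recorded.
4. State the score range and whether >9 means the top score only.

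The cost is wording in the outcome and analysis sections. The same scores at the same looks are used, with no added assessments or patients. The downside is that a median or a proportion replaces a mean time, and if more than half of an arm is unreached the median for that arm cannot be estimated.
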